7.8.3 Vital signs

The analysis of vital signs will be descriptive in nature. Descriptive statistics of vital signs over time and for the difference from baseline (see [Section 6.7](#)) will be provided.

Unscheduled measurements of vital signs will be assigned to planned time points in the same way as described above for laboratory data. However, for vital signs, descriptive statistics will be calculated by planned time point based on the last value of the subject at that planned time point (or assigned to that planned time point).

Clinically relevant findings in vital signs data will be reported as baseline conditions (at screening) or as AEs (during the trial) if judged clinically relevant by the investigator, and will be analysed as such.

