Test product: BI 730357 BS (C-14) oral solution dose: 50 mg 
• In 10 mL oral solution (5 mg/mL)• containing a radioactive dose of approximately 3.7 MBq (100 µCi)				
mode of admin.: Oral with 240 mL of water after an overnight fast of at least 10 h				
Comparator product: Not applicable				
Duration of treatment: Single dose				

Proprietary confidential information © 2018 Boehringer Ingelheim International GmbH or one or more of its affiliated companies

Name of company: Boehringer Ingelheim		Tabulated Trial Protocol		
Name of finished product: Not applicable				
Name of active ingredient: BI 730357				
Protocol date: 27 July 2018	Trial number: 1407-0031		Revision date: 25 September 2018	
Criteria for pharmacokinetics: Primary endpoints: Mass balance recovery of total [¹⁴ C]-radioactivity in urine and faeces: Amount of radioactivity excreted as a percentage of the administered dose (fe _{0-t2}) for urine and faeces, fe _{urine, 0-t2} and fe _{faeces, 0-t2} Secondary endpoints: Assessment of the pharmacokinetics of an oral solution formulation of BI 730357 BS (C-14) by calculation of the following parameters for total [¹⁴ C]-radioactivity and BI 730357 in plasma: C _{max} and AUC _{0-tz}				
Criteria for safety: Adverse events (AEs) including clinically relevant findings from the physical examination, safety laboratory tests, 12-lead electrocardiogram (ECG), vital signs (blood pressure [BP], pulse rate [PR])				
Statistical methods: Descriptive statistics and graphical displays				

FLOW CHART

Visit	Day	Planned time (relative to drug administration [h:min])	Approximate clock time of actual day [h:min]	Event and comment	Safety laboratory	PK blood / plasma ²	PK urine ⁶	PK faeces ⁷	Blood sampling for metabolic profiling ¹⁶	12-lead ECG	Vital signs (BP, PR)	Questioning for AEs and concomitant therapy ⁹
1	-21 to -1			Screening (SCR) ¹	x					x	x	
2	-2	-48:00	08:00									
	-1	-18:00	14:00	Admission to trial site	x ⁵							
		-14:00	18:00	Light Supper (voluntary)								
		-10:30	21:30	Snack (voluntary) ¹⁷								
1	-2:00	06:00			x ³	x ^{3,15}			x ³	x ³	x ³	
	0:00	08:00	Drug administration				▲	▲				
	0:30	08:30			x							
	1:00	09:00			x				x			
	1:30	09:30			x							
	2:00	10:00	240 mL fluid intake		x ⁸	x			x			
	4:00	12:00	240 mL fluid intake, thereafter lunch ⁴		x ⁸	x	+		x	x	x	
	8:00	16:00	Snack (voluntary) ⁴			x	+		x			
	11:00	19:00	Dinner									
	12:00	20:00			x ⁸	x	+		x	x	x	
	2	24:00	08:00		x ⁸	x	+	+	x			x

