6. INVESTIGATIONAL PLAN

6.1 VISIT SCHEDULE

Exact times of measurements outside the permitted time windows will be documented. The acceptable time windows for screening and end-of-trial examination are given in the [Flow Chart](#).

Study measurements and assessments scheduled to occur ‘before’ trial medication administration on Day 1 are to be performed and completed within a 3 h-period prior to the trial drug administration.

The acceptable deviation from the scheduled time for vital signs, ECG and laboratory tests will be \pm 30 min on Day 1 and \pm 90 min from Day 2 onwards in Visit 2.

If several activities, including ECG and meal intake, are scheduled at the same time point in the [Flow Chart](#), ECG should be the first and meal the last activity. Furthermore, if several measurements including venipuncture are scheduled for the same time, venipuncture should be the last of the measurements due to its inconvenience to the subject and possible influence on physiological parameters.

For planned individual plasma/blood concentration sampling times and urine/faeces sampling times or collection intervals refer to the [Flow Chart](#). While these nominal times should be adhered to as closely as possible, the actual sampling times will be recorded and used for determination of pharmacokinetic parameter. If beginning or end of a urine/faeces collection interval and a blood sample are scheduled for the same time point, urine/faeces collection should be done first, with withdrawal of the blood sample as close to the planned time point as possible.

If a subject misses an appointment, it will be rescheduled if possible. The relevance of measurements outside the permitted time windows will be assessed no later than at the Blinded Report Planning Meeting.

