6.7 BASELINE, TIME WINDOWS AND CALCULATED VISITS

The last non-missing value determined prior to the first study drug administration will be defined as baseline.

Time windows are defined in Section 6.1 of the CTP. Adherence to time windows will be checked at the RPM/DBLM.

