7.8.2 Laboratory data

The analyses of laboratory data will be descriptive in nature and will be based on BI standard "Display and Analysis of Laboratory Data" ([10](#)). Alpha-1 Acid Glycoprotein values will only be listed.

Analyses will be based on normalised values, which means transforming to a standard unit and a standard reference range.

Descriptive statistics of laboratory values over time and for the difference from baseline (see [Section 6.7](#)) will be provided. Frequency tables of changes between baseline and last value on treatment with respect to the reference range will be presented.

Unscheduled measurements of laboratory data will be assumed to be repeat measurements of the most recent scheduled measurement (e.g. for follow-up or confirmation of a particular value). Therefore, unscheduled measurements will be assigned to the planned time point of the previous scheduled measurement. Descriptive statistics will be calculated by planned time point based on the worst value of the subject at that planned time point (or assigned to that planned time point).

Possibly clinically significant abnormal laboratory values are only those identified either in the Investigator's comments on the eCRF or at the RPM/DBLM at the latest. It is the Investigator's responsibility to decide whether a lab value is clinically significant abnormal or not. Standard or project-specific rules for flagging clinically significant values will not be applied in this study.

Clinically relevant findings in laboratory data will be reported as AEs and will be analysed as part of AE analysis.

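### Vital-sign tables keep only the last reading assigned to a time point, with no limit on lateness, so a reading up to 13.5 days later can stand as the 12 h value

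*SAP*

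**What the plan says.** SAP 7.8.3 covers vital signs in two steps.

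- **Assignment.** "Unscheduled measurements of vital signs will be assigned to planned time points in the same way as described above for laboratory data". The laboratory rule in SAP 7.8.2 is that "unscheduled measurements will be assigned to the planned time point of the previous scheduled measurement". Neither section sets a maximum interval.
- **Choice of value.** For vital signs, "descriptive statistics will be calculated by planned time point based on the last value of the subject at that planned time point", and the sentence goes on to include values assigned to that point. Laboratory summaries differ: they are "based on the worst value of the subject at that planned time point".

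The same section promises descriptive statistics over time and for the difference from baseline. SAP Table 6.1: 1, whose title names vital signs, ends the on-treatment phase at midnight after a residual effect period (REP) of 7 days; later data belong to follow-up.

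The protocol Flow Chart plans vital signs at screening, 2 h before dosing, 4 h, 12 h, Day 15 (336 h) and the end-of-trial visit.

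**The concern.** Nothing in SAP 7.8.3 protects the scheduled reading. Once an unscheduled reading has been assigned to a time point it is later than the scheduled one, so it becomes the value that is summarised. If there are several, the latest is used.

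This matters most for the 12 h point because the next planned reading is almost two weeks away. A blood pressure taken on Day 10 for some unrelated reason would enter the table as the 12 h value, and its difference from baseline would be reported as the 12 h change. The 4 h and 12 h rows are the only planned post-dose vital signs before the Day 15 discharge reading, so they are where the tables would show a short-term effect on blood pressure or pulse. A mislabelled value there gives a wrong description of that time point.

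**Working it through.** **Step 1: planned vital-sign times.** I read the Flow Chart by column. Some Day 1 rows are shifted in the extracted text, so I checked the column order against the laboratory times in the footnotes to protocol Table 5.2.3: 1 and the metabolic-profiling times in Table 5.5.2: 3. Post-dose vital signs fall at 4 h, 12 h, 336 h and end of trial. The 24 h row has laboratory, PK, excreta, metabolic-profiling and AE-questioning marks, but no ECG or vital signs. The 168 h row has laboratory, PK and excreta marks only.

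**Step 2: span that each label absorbs under the assignment rule.**

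| Label in the table | Takes unscheduled readings from | until | Span |
|---|---|---|---|
| 4 h | 4 h | 12 h | 12 − 4 = 8 h |
| 12 h | 12 h | 336 h | 336 − 12 = 324 h; 324 / 24 = 13.5 days |
| 336 h | 336 h | end-of-trial visit | depends on the visit date |

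The 12 h label covers 324 / 336 = 96% of the in-house period after dosing, including all of Days 2 to 14.

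**Step 3: analysis phase.** Dosing is on Day 1, so a REP of 7 days ends on Day 8 and the on-treatment phase closes at midnight at the start of Day 9. With the Flow Chart's approximate dosing time of 08:00, 192 h is 08:00 on Day 9, so that midnight is 192 − 8 = 184 h. Of the 324 h carried by the 12 h label, 336 − 184 = 152 h lie in follow-up by Table 6.1: 1. A reading from those hours would still be summarised as the 12 h value.

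**Step 4: possible size.** The documents give no figure for how often unscheduled readings occur or how far they differ from scheduled ones, so the differences below are assumptions. If one subject's value is replaced by one that differs by d and the other subjects are unchanged, the mean moves by d / n. With the planned n = 6:

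- d = 10 mmHg: 10 / 6 = 1.7 mmHg
- d = 20 mmHg: 20 / 6 = 3.3 mmHg
- d = 30 mmHg: 30 / 6 = 5.0 mmHg

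The extremes can move further. If that subject's scheduled change was +30 mmHg, the others' was 0 and the later reading shows 0, the tabulated maximum change falls from 30 to 0. With no unscheduled reading, the table is unaffected.

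**The case against.** There is a fair case for leaving the rule alone. Vital signs are descriptive further parameters in a mass-balance trial with no hypothesis tests (protocol 5.2.1 and 7.2), and no primary or secondary endpoint is touched. Last value looks like a deliberate choice, since the SAP contrasts it with the laboratory rule. Assigning unscheduled readings to the prior time point also matches the protocol's handling of ECGs in 5.2.4.1. SAP 6.2 sends time-window listings to the report planning meeting, which may decide whether a discrepant value can be used. All of this limits the importance of the point. It does not make a Day 10 reading a 12 h reading, and the review in SAP 6.2 does not expressly cover unscheduled measurements.

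A reader might infer stronger points, which the documents do not support:

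- **That the rule contradicts the visit windows.** SAP 6.7 says "Time windows are defined in Section 6.1 of the CTP", and protocol 6.1 begins "The acceptable deviation from the scheduled time for vital signs, ECG and laboratory tests will be" before giving ± 30 min on Day 1 and ± 90 min later in Visit 2. Those limits apply to scheduled readings. An unscheduled reading has no scheduled time to deviate from, so there is no literal conflict.
- **That an acute effect would vanish from the report.** SAP 7 lists every subject's individual values, and with six subjects (eight at most) the listing is easy to read. SAP 7.8.3 also reports findings judged clinically relevant as adverse events.
- **That replacement always favours normal values.** Protocol 6.2.3 follows clinically relevant abnormal values until they are acceptable, so the last of those may well be near normal; but those are the findings also reported as adverse events. For other re-checks the documents give no direction, and a worse later reading would be kept.

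**Conclusion.** The point holds as a minor one. Followed as written, SAP 7.8.3 lets the latest unscheduled vital sign replace the scheduled reading. At 12 h that reading may be up to 13.5 days late and may fall after the on-treatment phase. At 4 h it may be up to 8 h late. This is a stated rule that can mislabel a tabulated result, not a missing detail.

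The consequence stays within descriptive summaries and differences from baseline. The shift of 3.3 to 5.0 mmHg in a mean of six rests on an assumed difference of 20 to 30 mmHg in one subject. The conclusion about timing rests only on the Flow Chart and the SAP text. The listings and adverse event reporting keep the underlying information.

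**What to change.** Amend SAP 7.8.3 for post-dose time points as follows:

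- Base by-time-point statistics and differences from baseline on the scheduled reading.
- Use a repeat only when the scheduled reading is missing or technically invalid and the repeat lies within the protocol 6.1 window.
- List all other unscheduled readings at their actual time, and do not let them replace a scheduled value.
- Optionally, add each subject's lowest and highest on-treatment value, using all readings, so that an unscheduled extreme appears in a table as well as in the listing.

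A time limit alone would not be enough. If the last reading within ± 30 min were kept, a re-check made minutes after an unusual 4 h or 12 h value would still overwrite it.

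The cost is SAP wording and minor programming, with a small departure from the sponsor's standard rule. No new data and no protocol amendment are needed.

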7.8.4 ECG

Abnormal findings in 12-lead ECG will be reported as baseline conditions (at screening) or as AEs (during the trial) if judged clinically relevant by the investigator, and will be analysed as such. No separate listing or analysis of ECG data will be prepared.

7.8.5 Others

Physical examination findings will be reported as relevant medical history/baseline condition (i.e., a condition already existent before intake of first study drug) or as AE and will be summarised as such. No separate listing or analysis of physical examination findings will be prepared.

10. HISTORY TABLE

Table 10: 1 History table

Version	Date (DD-MMM-YY)	Author	Sections changed	Brief description of change
Final	10-JAN-2019		None	This is the final TSAP without any modification
